#### 10.3 SAE Documentation and Reporting

Any event meeting the definition of an SAE must be documented using the paper MCC SAE Report Form.

Any event meeting the definition of serious must be reported to Masonic Cancer Center Multisite Program Manager within 24 hours of knowledge. Refer to Section 10.6.

#### 10.4 Dose Limiting Toxicity and Excessive Toxicity (Stopping Rule Events) Documentation and Reporting Requirements

All patients enrolled in Components 1 and 2 are monitored for dose limiting toxicity (DLT) and excessive toxicity (early stopping events) specific to the Component. Refer to Section 12 for definitions. (ONLY POST FT596 EVENTS COUNT)

In addition to documenting the event in the study's CRF's, all DLT and SR events are to be documented on the Event Form found in OnCore per Masonic Cancer Center procedures.

An event that counts as a DLT does not necessarily constitute a SAE and should be reported as such only if they meet the criteria for reporting as defined in Section 10.5.

#### **10.5 Documentation of Death and Reporting Requirements**

Deaths during the treatment and follow-up period, including due to disease, will be recorded as an SAE and reported per Section 10.6. Deaths due to disease should be recorded as a Grade 5 Neoplasm.

In addition, the death date and cause must be documented in the patient follow-up tab in OnCore upon knowledge using the comment field in the survival status section to record the cause.

Event Type	Reporting Timeframe	Form to Use	Report to
Any event meeting the	Within 24 hours of	Paper SAE	For Participating Sites:
definition of serious and all	knowledge	Report Form	Masonic Cancer Center (MCC)
patient deaths			Multisite Program Manager
Dose Limiting Toxicities	Within 24 hours of	DLT Event Form	[contact]
	knowledge	in OnCore	
Stopping Rule Events	Within 24 hours of	Stopping Rule	Local institutional IRB or other
(Excessive Toxicity)	knowledge	Event Form in	entities per institutional policies
		OnCore	and guidelines
Major Deviations, as	Within 5 working days	Deviation Report	
defined in Section 10.1 .	of knowledge	Form in OnCore	
Minor Deviations as	Per Institutional Policy	n/a (record in	For LIMN MCC: Report to the
defined in Section 10.1	T el manalonal T olley	Deviations Tab)	study's regulatory specialist
		Deviatione rub)	orady o regulatory oppositilior
			For Participating Sites: minor
			deviations are not reportable to
			the MCC Multisite Manager.
			Report to local institutional IRB or
			other entities per institutional
			policies and guidelines.

#### **10.6 Institutional Event Reporting Table**

\*events occurring at the University of Minnesota are reported to the study's Regulatory Specialist who will submit to other entities as usual

Individual institutional sites are responsible for reporting any event meeting local reporting requirements to their institutional IRB and/or other research oversight committees.

#### **10.7 Expedited MCC Reporting Requirements (MCC)**

As the study sponsor, the Masonic Cancer Center has the following expedited reporting responsibilities for select events reported in Section 10.6:

Agency reporting to	Criteria for reporting	Timeframe	Form to Use	Submission address/email address
Advarra (IRB of Record)	unanticipated problems involving risks to subjects or others; unanticipated adverse device effects; protocol violations that may affect the subjects' rights, safety, or well-being and/or the completeness, accuracy and reliability of the study data; subject death; suspension of enrollment; or termination of the study	promptly and no later than 2 weeks (10 business days) from the time the investigator learns of the event	Refer to the Advarra IRB Handbook	Advarra via study specific CIRBI Link
UMN IRB	Refer to Submitting Updates in ETHOS – External IRB Stu	dy/Site		
FDA	Unexpected and fatal or unexpected and life threatening suspected adverse reaction 1) Serious and unexpected suspected adverse reaction or 2) increased occurrence of serious suspected adverse reactions over that listed in the protocol or investigator brochure or 3) findings from other sources (other studies, animal or in vitro testing)	no later than 7 Calendar Days no later than 15 Calendar-Days	MCC SAE Report Form	Submit to FDA as an amendment to IND with a copy to each participating site and Fate Therapeutics
	
 
All other events per CFR 312.33
 
An annual manufacturing update, including for each new lot of the investigational biologic used in clinical trials, the lot number, the results of all tests performed on the lot, and the specifications when established (i.e., the range of acceptable results) (21 CFR 312.23(a)(7))
 
	At time of IND annual report	Summary format	Submit as part of the IND annual report
U of MN Institutional Biosafety Committee	Any significant research-related accidents and illnesses involving potentially hazardous biological agents subject to IBC purview	As soon as possible (within 24 hours is ideal)	IBC Incident Report	Via eProtocol

### 11 Study Data Collection and Monitoring

#### 11.1 Data Management

This study will collect regulatory and clinical data using University of Minnesota CTSI's instance of OnCore® (Online Enterprise Research Management Environment).

The OnCore database resides on dedicated secure and PHI compliant servers. All relevant AHC IS procedures related for PHI compliant servers (as required by the Center of Excellence for HIPAA Data) apply to OnCore databases. The informatics team grants the IRB approved study team members access to data.

Additional immune monitoring data about correlative laboratory samples generated by the Masonic Cancer Center Translational Therapy Laboratory (TTL) from the protocol-directed correlative research samples is stored in their Laboratory Information Management System (LIMS). The LIMS database application is also stored on a production server located in the UMN datacenter (WBOB) and is managed by the Academic Health Center

Key study personnel are trained on the use of OnCore and will comply with protocol specific instructions embedded within the OnCore.

#### 11.2 Case Report Forms

Participant data will be collected using protocol specific electronic case report forms (e-CRFs) developed within OnCore based on its library of standardized forms. The e-CRF will be approved by the study's Principal Investigator and the Biostatistician prior to release for use. The Study Coordinator or designee will be responsible for registering the patient into OnCore at time of study entry, completing e-CRFs based on the patient specific calendar, and updating the patient record until patient death or end of required study participation.

#### 11.3 Data and Safety Monitoring Plan (DSMP)

The study's Data and Safety Monitoring Plan will be in compliance with the University of Minnesota Masonic Cancer Center's Data & Safety Monitoring Plan (DSMP), which may be accessed at http://z.umn.edu/dmsp.

For the purposes of data and safety monitoring, this study is classified as high risk (under a locally held IND). Therefore, the following requirements will be fulfilled at the University of Minnesota and at participating sites:

- At least quarterly review of the study's progress by the Masonic Cancer Center Data and Safety Monitoring Council (DSMC).
- The University of Minnesota (lead site) Principal Investigator will comply with at least twice yearly monitoring of the project by the Masonic Cancer Center monitoring services.
- The local site PIs will comply with at least twice yearly monitoring of the project by each site's internal monitoring staff.
- The University of Minnesota (lead site) Principal Investigator will oversee the submission of all reportable adverse events per Section 10.7 to the Masonic Cancer Center's SAE Coordinator, the University of Minnesota IRB; and oversee the submission of all reportable adverse events to the FDA
- The University of Minnesota (Sponsor) and the MCC CTO have oversight responsibility for trial monitoring at affiliate sites.

#### IND Annual Reports

In accordance with regulation 21 CFR § 312.33, the IND sponsor ([name]) will submit a progress report annually. The report is submitted within 60 days of the anniversary date that the IND went into effect. A copy of the report will be provided to Fate Therapeutics. Additional annual reporting requirements are found in the FDA Acknowledgment of Receipt of IND dated March 25, 2020.

#### **11.4 Participating Site Monitoring**

The PI ([name]) with the CTO has oversight responsibility for trial monitoring at participating sites.

Participating sites must self-monitor using the Masonic Cancer Center Data and Safety Monitoring Plan (https://www.cancer.umn.edu/for-researchers/clinicalinvestigator-resources/mcc-dsmp). Alternately, participating sites that are an NCI designated Cancer Center may self-monitoring using their NCI approved Data and Safety Monitoring Plan.

The investigator will permit study-related monitoring, audits, and inspections by the study's Principal Investigator/IND sponsor and/or any designees, the local IRB, government regulatory bodies, and University of Minnesota compliance groups. The investigator will make available all study related documents (e.g. source documents, regulatory documents, data collection instruments, study data, etc.). The investigator will ensure the capability for inspections of applicable study-related facilities (e.g. pharmacy, diagnostic laboratory, etc.) will be available for trial related monitoring, audits, or regulatory inspections.

#### **11.5** Teleconferences – Lead Site and Participating Sites

Regular teleconferences will be held to facilitate communication between participating sites regarding the study's progress, patient updates, summary of safety reports, case report form completion, and other issues for discussion. The University of Minnesota Participating Sites Manager is responsible for arranging these teleconferences and preparing the agenda. Meetings will occur every 2 weeks; however, these may be scheduled more or less frequently at the discretion of the lead institution. Participation of a minimum of one representative from each affiliate site is expected. These teleconferences are in addition to other previously described site interactions including centralized patient registration, institutional and MCC required reporting of safety related issues, case report form completion in the study's central database (OnCore) and affiliate oversight through self-monitoring in compliance with the Masonic Cancer Center's Data and Safety Monitoring plan.

#### 11.6 Record Retention

The investigator will retain study records including source data, copies of case report forms, consent forms, HIPAA authorizations, and all study correspondence in a secured facility until permission is received that the documents are no longer needed.

Please contact the CTO before destroying any study related records.

#### **12 Statistical Considerations**

#### 12.1 Study Designs

This study consists of two components. The 1st component is a Phase I clinical trial to identify the maximum tolerated dose (MTD) of FT596 at Day 30 post FT596 infusion. The second component is a Phase I clinical trial to identify the MTD of FT596 at Day 7 post FT596 infusion. Rituximab is given 2-3 days before FT596. In addition to identifying the MTD and providing preliminary estimates of safety, secondary objectives include providing preliminary descriptive estimates of efficacy such as progression-free survival, relapse and non-relapse mortality along with their error measurements. Correlative objectives include measurement of the persistence of FT596 in blood after each FT596 infusion by immunophenotyping and PCR up to 1 year, the association of FT596 persistence with safety and anti-tumor activity.

Component 1 will identify the MTD of FT596 when given as a single dose at Day 30. Up to three FT596 dose levels are planned (Dose Level 1:  $9x10^7$  cells/dose, Dose Level 2:  $3x10^8$  cells/dose, Dose Level 3:  $9x10^8$  cells/dose with a Dose Level - 1:  $3x10^7$  cells/dose tested only if DLT at DL1).

**Component 1 dose limiting toxicity** is defined as any of the following events within 28 days after the FT596 dosing based on CTCAE v5:

- Grade 4 hematologic toxicity lasting > 7 days (not including lymphopenia)
- Grade 4 non-hematologic toxicity
- Grade ≥3 FT596 Infusion Related Reaction
- Grade 2 acute GVHD that requires steroid therapy >7 days or progression after 3 days of steroids or has partial response after 14 days of treatment
- Grade ≥3 acute GVHD
- Grade 4 cytokine release syndrome (CRS)
- Grade 3 CRS that does not resolve to < Grade 2 in 72 hours
- Grade 3 neurotoxicity

- Grade 3 organ toxicity involving vital organs; cardiac, central nervous system and pulmonary that lasts for longer than 7 days including Grade 3 Investigations (laboratory values) of any duration that indicate damage to vital organs.
- Any Grade 3 non-hematological toxicity that does not resolve to ≤Grade 2 within 72 hours; excepting Grade 3 renal and hepatic toxicity which may take up to 7 days to resolve to ≤Grade 2

The MTD will be determined by using a modified Continual Reassessment Method (CRM). (Goodman 1995) The CRM uses a power model for the probability of DLT at each dose, where the probability of toxicity at dose i is modeled as  $piexp(\alpha)$  where pi is a constant and  $\alpha$  is distributed a priori as a normal random variable with mean 0 and variance 2. The goal of this CRM will be to identify one of the 3 dose levels corresponding to the desired maximum acceptable toxicity rate of ≤25%.

Initial estimates of toxicity or the "skeleton" estimates are provided by the clinician. The initial estimates or prior probability of toxicity are listed as 1%, 3%, and 6% for doses 1, 2 and 3, respectively. As the study progresses, the CRM will continually update the estimates of the toxicity probabilities.

Patients are enrolled in cohorts of 3 starting at Dose Level 1. A minimum of 28 days will separate each cohort. For Dose Level 1 a minimum of 28 days will separate each patient to assess for dose limiting toxicity (DLT). In subsequent cohorts, the 1st and 2nd patient will be separated by at least 28 days and at least 14 days will separate the 2nd and 3rd patient. Enrollment will continue in cohorts of 3 and each new cohort of 3 will be sequentially assigned to the most appropriate dose based on the updated toxicity probabilities after the 3rd patient from the previous cohort has reached 28 days. The MTD will be identified when the total sample size of 18 is exhausted or 6 patients are sequentially enrolled at the same dose. A maximum of 18 patients is used in part due to low expected toxicity. The function 'crm' from the R package 'dfcrm' will calculate posterior means of toxicity probabilities. The CRM uses a Bayesian framework that combines experience from patients in the earlier part of the trial with the clinician's initial best estimate of the toxicity rates at each dose level to estimate a dose level that best corresponds to the target toxicity of ≤25%. Dose escalation of more than one level is not permitted with this design.

Component 2 will use a similar design but identify the MTD of FT596 when given as a single dose at Day 7. Up to two dose levels of FT596 are planned (1 Dose Level below the MTD from component 1 and the MTD from component 1) so any two sequential dose levels of the following may be included (Dose Level -1:  $3x10^7$  cells/dose, Dose Level 1:  $9x10^7$  cells/dose, Dose Level 2:  $3x10^8$  cells/dose, Dose Level 3:  $9x10^8$  cells/dose).

The DLT events for Component 2 are the same as in Component 1 except for the addition of:

• Non-engraftment by Day 28 post-transplant

The MTD will be identified in the same fashion as Component 1 except that the initial estimates or prior probability of toxicity may be slightly higher due to the infusion of cells at Day 7 plus the additional possible DLT event. Assuming that we start at Dose Level 2, the skeleton probabilities might be listed as 5% and 10% for doses 2 and 3, respectively. The target toxicity level will still be  $\leq 25\%$ . As in Component 1, the CRM will continually update the estimates of the toxicity probabilities of both doses; first at the end of 28 days post infusion for each of the first three patients; and at the end of the of 28 day follow-up for the last patient in each of the 3 patient cohorts beyond the initial 3 patients. A minimum of 28 days will separate each patient in the 1st cohort to assess for dose limiting toxicity (DLT). In subsequent cohorts, the 1st and 2nd patient will be separated by at least 28 days and at least 14 days will separate the 2nd and 3rd patient.

As in Component 1, each new cohort of three patients will be sequentially assigned to the most appropriate dose based on the updated toxicity probabilities, and the MTD will be identified when a total sample size of 18 is exhausted or 6 patients are sequentially enrolled at the same dose.

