#### \*Dose Levels for Identification of MTD

Dose Level	FT596 Cells per Dose	Enrollment Plan
-1	3 x 10  cells	Tested only if Dose Level 1 has DLT
1 (start)	9 x 10  cells	Enroll 3 patients at Dose Level 1 with at least 28 days between each of the 3
2	3 x 10  cells	patients. Once the 28 day DLT assessment periods ends for all 3 patients,
3	9 x 10  cells	enroll the next cohort of 3 patients to the most appropriate dose based on the updated toxicity probabilities. A minimum of 28 days must separate the 1 st and 2 nd patients and a minimum of 14 days must separate the 2 nd and 3 rd patient within a cohort. The MTD is identified when the total sample size of 18 is exhausted or 6 patients are sequentially enrolled at the same dose.

**Component 1 dose limiting toxicity** is defined as any of the following events within 28 days after FT596 dosing based on CTCAE v5:

- Grade 4 hematologic toxicity lasting > 7 days (not including lymphopenia)
- Grade 4 non-hematologic toxicity
- Grade ≥3 FT596 Infusion Related Reaction
- Grade 2 acute GVHD that requires steroid therapy >7 days or progression after 3 days of steroids or has partial response after 14 days of treatment
- Grade ≥3 acute GVHD
- Grade 4 cytokine release syndrome (CRS)
- Grade 3 CRS that does not resolve to < Grade 2 in 72 hours
- Grade 3 neurotoxicity
- Grade 3 organ toxicity involving vital organs; cardiac, central nervous system and pulmonary that lasts longer than 7 days including Grade 3 Investigations (laboratory values) of any duration that indicate damage to vital organs.
- Any Grade 3 non-hematological toxicity that does not resolve to ≤Grade 2 within 72 hours; excepting Grade 3 renal and hepatic toxicity which may take up to 7 days to resolve to ≤Grade 2

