#### 12.2 Sample Size

Due to the low expected toxicity, a maximum of 18 patients will be enrolled during component 1. Based on the simulations from table 1, this should be sufficient and safe to define the MTD for component 1. Based on the simulations from table 2, component 2 should also be sufficient and safe to define the MTD. Enrollment will most likely include 12 patients under each component but could range from 2 to 18 patients. With expected enrollment of 12-18 patients/year, accrual for each component should be complete within 1.5 years. So after combining both trials, accrual should be complete in 2.5-3 years.

	Expected DLT			Excessive DLT			
Cells/	True	Probability of	Patient	True	Probability of	Patient	
dose	Probability	dose	Number	Probability	selecting dose	Number	
9x10 	1%	0%	3	10%	15%	6	
3x10 	3%	0%	3	25%	51%	6	
9x10 	6%	100%	6	40%	34%	6	

 Table 1. Operating characteristics for CRM (component 1)

	Expected DLT			Excessive DLT			
Cells/	True	Probability of	Patient	True	Probability of	Patient	
dose	Probability	dose	Number	Probability	selecting dose	Number	
3x10 	5%	0%	6	25%	74%	6	
9x10 	10%	100%	6	40%	26%	6	

Table 2. Operating characteristics for onthe (intery section). component 2
--

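### Dose Level -1 sits outside the Component 1 CRM, so the stated rule can neither assign nor select it, and no rule declares that there is no MTD when Dose Level 1 is too toxic

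*Combined protocol and SAP*

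**What the plan says.** The Study Schema table of dose levels gives Dose Level -1 one instruction of its own: "Tested only if Dose Level 1 has DLT". Section 12.1 repeats it ("tested only if DLT at DL1"), as do the Synopsis, Section 3 and Section 6.2.

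Section 12.1 then sets out a power-model CRM. Its aim is "The goal of this CRM will be to identify one of the 3 dose levels" that meets the 25% limit. The prior DLT probabilities are "1%, 3%, and 6% for doses 1, 2 and 3, respectively". Cohorts of three follow the updated probabilities, and the model looks for "a dose level that best corresponds to the target toxicity of ≤25" percent. The MTD is fixed at 18 patients, or once "6 patients are sequentially enrolled at the same dose". Moving up more than one level is barred; nothing is said about moving below Dose Level 1.

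Section 12.2 concludes: "Based on the simulations from table 1, this should be sufficient and safe to define the MTD for component 1". Table 1 has rows for Dose Levels 1 to 3 only, with Dose Level 1 at a true rate of 1% or 10%. The section adds: "Enrollment will most likely include 12 patients under each component but could range from 2 to 18 patients". It does not describe how a component would end at the low end of that range.

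**The concern.** The Component 1 MTD is the primary objective and fixes both Component 2 doses. Section 7 says there are no clinical data on FT596, so the 1% prior for Dose Level 1 is a clinician's estimate. The sponsor listed a lower dose in case that estimate is wrong, but a dose without a prior value gets no updated probability, and cohorts are assigned by those probabilities. If Dose Level 1 proves too toxic, the stated rule cannot move patients down or conclude that no studied dose is acceptable.

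**Working it through.** **Inputs (Section 12.1).** P(DLT at dose i) = p_i^exp(α), with α ~ N(0, variance 2) and p = 0.01, 0.03, 0.06. Target 25%, cohorts of three, start at Dose Level 1, no skipping upward, maximum 18, six-in-sequence stop. I used exact enumeration. The next dose is the one whose estimate is closest to 25%. I took both estimators: plug-in of the posterior mean of α, and the posterior mean of each probability, which is the quantity Section 12.1 names.

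**The plan's own figure.** If six in sequence ends the trial only when the CRM also recommends staying, the Expected column gives 0.1/0.1/99.8% selected and 3.1/3.0/6.0 patients (plug-in). Table 1 has 0/0/100% and 3/3/6, so a three-level CRM reproduces that column. The Excessive column (15/51/34%) did not reproduce: 26/28/46% under this stop, 20/44/36% with 18 patients always enrolled. The plan does not give the number of simulations or the exact selection rule, so this does not show the column to be wrong.

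**What Table 1 allows as an outcome.** In the Excessive column, 15 + 51 + 34 = 100% of selections and 6 + 6 + 6 = 18 patients go to Dose Levels 1 to 3. Dose Level -1 and no MTD are not possible results.

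**Estimates after the first cohort.** From the plug-in estimate at Dose Level 1, exp(α) = ln(estimate)/ln(0.01), which gives the other two. After 1/3: ln(0.272)/ln(0.01) = 0.283, 0.03^0.283 = 0.371, 0.06^0.283 = 0.451.

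| DLTs at Dose Level 1 | DL1, plug-in | DL1, posterior mean | DL2, plug-in | DL3, plug-in |
|---|---|---|---|---|
| 1/3 | 27.2% | 28.8% | 37% | 45% |
| 2/3 | 51.5% | 49% | 60% | 67% |
| 3/3 | 71.7% | 68% | 78% | 82% |

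The model rises with dose. Once the Dose Level 1 estimate passes 25%, Dose Level 1 is always the closest modelled dose, however high its estimate.

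**How often Dose Level 1 is named MTD when it is too toxic.** The true rates here are my assumptions. Plug-in results, Dose Level -1 never used, no halts:

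| True DL1/2/3 | Dose with six in sequence is MTD | Stop only if CRM also stays | CRM choice after the sixth is MTD |
|---|---|---|---|
| 30/40/50% | 82.3% | 80.6% | 67.8% |
| 40/55/65% | 95.4% | 96.4% | 86.7% |
| 50/60/70% | 98.4% | 99.0% | 94.1% |

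With both estimators, the 40% row spans about 87-97%.

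**How likely the situation is under the sponsor's rates.**
- At least one DLT in three, 1 - (1 - p)^3: 3.0% at p = 1%, 27.1% at p = 10%.
- Two or more in three, 3p²(1 - p) + p³: 3(0.0001)(0.99) + 0.000001 = 0.03% at 1%; 3(0.01)(0.9) + 0.001 = 2.8% at 10%.

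**The case against.** **Other controls apply.** Under Sections 12.4.1 to 12.4.3, a death by Day 100, Grade III-IV acute GVHD or a Grade 4 infusion reaction halts enrollment for review. Grade 4 DLTs do so at two (Section 12.4.4), or at any one as listed in the Synopsis, Study Schema and Section 6.4. FDA reviews the data before Component 2, which would start one level below the MTD. This limits the harm and stands as mitigation. But the halts end in review and possible restart: none assigns a dose or says when there is no MTD. DLTs such as Grade 3 neurotoxicity or unresolved Grade 3 CRS trigger none of them. FDA review comes after Component 1 has allocated its patients.

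**The toxic scenarios are far from the sponsor's expectation.** That is so. Rates of 30-50% are assumptions, against 1% and 10% in Table 1, and the cited source for the modified CRM is not available to me.

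**Stronger readings that the documents do not support.**
- A reader might infer that the trigger and the CRM conflict after one DLT in three. They do not. The trigger is a necessary condition: it makes Dose Level -1 available, and the CRM may still choose Dose Level 1.
- A reader might infer that any DLT sends the trial to Dose Level -1 for good. No text says so.
- A reader might infer that Dose Level -1 has no cohort rule at all. The Study Schema lists it in the same table as the cohort-of-three and six-in-sequence rules. What it lacks is the modelled probability those assignments use.
- A reader might take 25% as a strict ceiling. Then no modelled level would qualify after 1/3, and no next step is given. The best-corresponds wording favors the closest-dose reading used here.

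**Conclusion.** The point holds as a gap in the primary decision rule and should be fixed. Confidence in the omission is high: the CRM covers three levels, Dose Level -1 is not among them, and no text ends Component 1 without an MTD. Table 1 therefore does not support the sufficient-and-safe conclusion for the case Dose Level -1 exists to cover, since it never sets Dose Level 1 above 10% and never uses the lower dose.

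The 87-97% figure is less certain. It rests on an assumed true rate of 40%, the closest-to-target rule and no halts. The halts would lower it by an amount the documents do not let me estimate. If the sponsor's rates are right, gross toxicity at Dose Level 1 is rare.

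**What to change.** 1. Add Dose Level -1 to the CRM as a fourth level with a clinician-supplied prior value below 1%. Start at Dose Level 1 as now, open Dose Level -1 only after a DLT there, and amend the three-level wording in Section 12.1.
2. Add a no-MTD rule, for example when the posterior probability that Dose Level -1's DLT rate exceeds 25% passes a cut-off set by the sponsor.
3. Re-run Table 1 with rows for Dose Level -1 and no MTD, and a scenario with Dose Level 1 above 25%. State the estimator and how the six-patient stop works. After 1/3, with a Dose Level -1 prior of 0.3-0.5%, plug-in estimates (19-22% against 27.2%) keep the trial at Dose Level 1, while posterior means (22-25% against 28.8%) move it down.
4. State what Component 2 does if Dose Level -1 is the MTD, since there is then no level below it.

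**Cost**, assuming a Dose Level -1 prior of 0.3-0.5% and a cut-off of 0.90. Ranges cover both estimators and two readings of the stop (six patients alone, or six plus a CRM recommendation to stay):

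| Scenario | Effect on mean sample size |
|---|---|
| Expected (1/3/6%) | 11.8-12.2 before, 11.8-12.3 after |
| Excessive (10/25/40%), 5% assumed at Dose Level -1 | rises by about 0.1 to 2.4 |
| 40% assumed at Dose Level 1, 15-25% at Dose Level -1 | about 7.6-8.7 before, 8.7-14.3 after |

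In the last scenario Dose Level 1 is named MTD in about 14-52% of trials, down from 95-97%. The price is that the 0.90 cut-off declares no MTD in about 5-18% of trials although Dose Level -1 is acceptable, so the sponsor should tune it. A cohort takes at least 28 + 14 + 28 = 70 days, or 10 weeks. The added time is then roughly (8.7 - 7.6)/3 x 10 = 4 weeks to (14.3 - 8.7)/3 x 10 = 19 weeks. The 18-patient maximum does not change. The rest is a simulation re-run and a wording amendment.

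### Table 1 Excessive and both Table 2 columns (Section 12.2) do not follow the six-patient stop, and Section 12.1 does not tie its MTD criterion to that stop

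*Combined protocol and SAP*

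**What the plan says.** Section 12.1 (Component 1) sets out a one-parameter power model with a normal prior on alpha (mean 0, variance 2), cohorts of three from Dose Level 1 (DL1), and no escalation by more than one level. "The initial estimates or prior probability of toxicity are listed as 1%, 3%, and 6% for doses 1, 2 and 3, respectively". On stopping: "The MTD will be identified when the total sample size of 18 is exhausted or 6 patients are sequentially enrolled at the same dose".

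The purpose is worded in two ways. One is a ceiling: "The goal of this CRM will be to identify one of the 3 dose levels" that meet the "desired maximum acceptable toxicity rate of ≤25" (per cent). The other is a target: "to estimate a dose level that best corresponds to the target toxicity of ≤25" (per cent). The dfcrm package is named for the posterior means.

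For Component 2, "the MTD will be identified when a total sample size of 18 is exhausted or 6 patients are sequentially enrolled at the same dose", and "the skeleton probabilities might be listed as 5% and 10% for doses 2 and 3, respectively". Component 2 starts one level below the Component 1 MTD.

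Section 12.2 concludes: "Based on the simulations from table 1, this should be sufficient and safe to define the MTD for component 1". It says the same of Component 2 from Table 2, and expects that each component will probably enrol 12 patients. The tabulated values, from lower to higher dose, are:

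| Column | True DLT rate (%) | Selected (%) | Patients |
|---|---|---|---|
| Table 1 Expected | 1/3/6 | 0/0/100 | 3/3/6 |
| Table 1 Excessive | 10/25/40 | 15/51/34 | 6/6/6 |
| Table 2 Expected | 5/10 | 0/100 | 6/6 |
| Table 2 Excessive | 25/40 | 74/26 | 6/6 |

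The Synopsis, Study Schema and Sections 3, 6.2 and 12.1 also provide for Dose Level -1 after a DLT at DL1. It has no skeleton value.

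**The concern.** The MTD is the primary result, and it sets the Component 2 starting level. Two things look wrong.

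First, the tables are the plan's stated support for the design being sufficient and safe, yet their patient numbers look impossible or implausible under the stop. If so, expected size, dose selection and exposure by dose are misdescribed.

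Second, the stop says when the MTD is identified, while the criterion describes what the model aims at. The text does not say whether the MTD is the dose the six patients received or the model's dose at that moment. It does not say whether 25% is a ceiling or a nearest target, or what follows if every estimate is above it. The same data could then support two MTDs and two Component 2 starting levels.

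**Working it through.** **Inputs (Section 12.1).** Probability of DLT at dose i is skeleton_i^exp(alpha), with alpha ~ N(0, variance 2). Skeletons are 1/3/6% (Component 1) and 5/10% (Component 2, the plan's example). Cohorts of 3 start at the lowest modelled dose without skipping. The trial stops at 6 consecutive patients at one dose, or at 18; at 18 without six in a row, the model's dose counts as the MTD in both readings. All DLT paths were enumerated exactly. Ranges span nearest-to-25% or highest-dose-at-or-below-25% assignment, and estimates taken as the posterior mean of the probability or as a plug-in of the posterior mean of alpha. Selection ranges also cover the six-patient dose and the model's dose.

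**Plan's figures against the rule.**

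| Column | Patients, plan | Patients, rule (mean) | Total, plan | Total, rule (mean) |
|---|---|---|---|---|
| Table 1 Expected | 3/3/6 | 3.1/2.9–3.2/5.3–5.9 | 12 | 11.6–11.9 |
| Table 1 Excessive | 6/6/6 | 4.7–5.0/2.9–4.0/1.7–3.5 | 18 | 10.0–12.0 |
| Table 2 Expected | 6/6 | 3.5–3.6/5.1–5.2 | 12 | 8.6–8.7 |
| Table 2 Excessive | 6/6 | 5.6/2.1–2.3 | 12 | 7.7–7.9 |

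Table 1 Expected patient numbers fit. Its top dose is selected in 88.5–97.0% of trials, against 100% tabulated.

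**Hand checks.**

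- *Table 2, 6/6.* With two doses, three patients per cohort and a start at the lower dose, 6/6 without an earlier stop needs the order low, high, low, high. That order has not triggered the stop, so the trial continues. Possible endings are 6/0, 3/6, 9/3, 6/9, 12/6 and 9/9.
- *Table 2 Expected.* P(at least one DLT in the first 3) = 1 − 0.95³ = 14.3%. One DLT in three already gives estimates of 31.4/39.5% (plug-in 30.3/39.9%), so cohort 2 stays at the lower dose and the trial stops at 6/0. Otherwise the next cohort goes to the upper dose and stays there with at most one DLT: 0.857 × (0.729 + 0.243) = 83.3% end at 3/6, which is 9 patients. Exactly 12 patients occur in 0.4–2.4%. The lower dose is selected in 14.7–16.7% (six-patient dose) or 3.7–22.4% (model's dose).
- *Table 2 Excessive.* P(stop at 6/0) = 1 − 0.75³ = 57.8%. Even if all other trials ran to 18, the mean total would be 0.578 × 6 + 0.422 × 18 = 11.1, below 12.
- *Table 1 Excessive.* P(at least one DLT in the first 3) = 1 − 0.9³ = 27.1%, and all of these stop at 6. The mean total is therefore at most 0.271 × 6 + 0.729 × 18 = 14.7, below 18.

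**Which dose is the MTD.**

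- *1/6 DLTs at DL1.* Estimates are 17.4/25.0/31.9% (plug-in 14.9/23.5/31.3%). The six-patient dose is DL1. The nearest-to-25% dose is DL2, which no patient has received.
- *2/6 DLTs at DL1.* Estimates are 30.8/39.8/47.1% (plug-in 30.1/40.1/48.0%). All exceed 25%, yet the stop is met and the text says the MTD will be identified.

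| Scenario (three-dose model) | Six-patient and model dose differ | No modelled dose ≤25% at the stop |
|---|---|---|
| Component 1 Expected | 3.2–10.8% | 0.12–0.14% |
| Component 1 Excessive | 33.1–47.1% | 12.1–16.4% |

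With nearest-dose assignment and posterior means, Component 1 Excessive selection is 39/17/44% if the MTD is the six-patient dose and 20/50/30% if it is the model's dose.

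**The case against.** **A criterion is given.** A reader might infer that the plan never says which dose is the MTD. That goes too far: Section 12.1 says the CRM determines the MTD, states the general aim and names the software. This leans towards the model's dose. What stands is that the aim is not tied to the stop and is worded both as a ceiling and as a target.

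**Dose Level -1 is missing from the percentages.** This stands as a limit. In Component 1 Excessive, 71–95% of the trials with no modelled dose at or below 25% contain a DLT at DL1 (11.6 of 16.4; 11.5 of 12.1), the event after which the plan provides for Dose Level -1. Under nearest-dose assignment, so do nearly half of the trials where the two readings differ (19.6 of 42.8; 19.4 of 39.9). The plan gives that level no model, so the percentages describe the three-dose model only. The comparison with Table 1 is like for like, because Table 1 lists the same three doses.

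**Some selection figures are near.** The model-dose reading above (20/50/30%) is within 5 points of 15/51/34%, and a ceiling rule with the six-patient dose gives 72.7/27.3% against 74/26%. Those two columns fail on patient numbers.

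**The simulations omitted the stop.** A reader might infer this, since a fixed 18-patient run (nearest dose, plug-in) comes within 7 points of all four selection columns. The documents do not support it: such a run cannot total 12 patients, as three of the four columns do.

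**The stated range of 2 to 18 patients.** A reader might call 2 an error because the rule needs six. It can describe enrolment halted early, for example after two Grade 4 DLTs under Section 12.4.

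**Safeguards.** The Section 12.4 halts and the FDA review before Component 2 limit harm. They do not define the MTD.

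**Conclusion.** The point holds in this form. Table 1 Excessive and both Table 2 columns are wrong as written for a design with the six-patient stop, and the statement that 12 patients is most likely does not hold for Component 2 Expected, where 83% of trials end at 9. The Table 1 Expected patient numbers do fit. Separately, the final-dose rule is ambiguous, and no conclusion is stated when every estimate exceeds 25%. The ambiguity matters little under Component 1 Expected and substantially under Component 1 Excessive.

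Assumptions: Patient Number is not defined in the tables and was read as a mean or a final allocation; the Component 2 skeleton is the plan's tentative example; Dose Level -1 and the Section 12.4 halts are not modelled. The impossibility of ending at 6/6 needs only the cohort size, the two doses, the starting dose and the stop.

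**What to change.** 1. Reconcile the Component 1 and Component 2 text of Section 12.1 into one final-dose rule tied to the stop: the six-patient dose or the model's dose, and in the latter case what is concluded if that level was never given.
2. Make the ceiling and target wordings of 25% agree.
3. State what is concluded when no modelled dose meets the plan's own limit.
4. Reconcile the Dose Level -1 entries (Synopsis, Study Schema, Sections 3, 6.2 and 12.1) with the three-dose model.
5. Rerun Tables 1 and 2 of Section 12.2 with the stop included and a no-MTD row, define Patient Number, and restate the expected enrolment of 12.

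The choice of rule is the sponsor's. The cost is protocol wording and a simulation rerun; no patients are added. The downside is less favourable table figures and some trials ending without an MTD. If 25% is read as a ceiling on the final estimate, that share is about 0.1% (Component 1 Expected), 12–16% (Component 1 Excessive), 3.4% (Component 2 Expected) and 55–56% (Component 2 Excessive), with the limits stated above. The last figure is largely expected, because the lower dose's true rate there is itself 25%.
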